3.2.5 Application group

Participants undergoing the GA will be instructed on how to *download* the application and how to use it. From there, all personal data must be entered into the application so that alerts, tips and incentives can be issued to each one, individually, as described in item 3.1 (application development).

3.2.6 Control group

The GC, in turn, will participate in a single lecture, in the first week of the intervention, with basic guidelines related to the key points of the treatment of SAH, including the importance of medication adherence, monitoring of blood pressure values and/or capillary glucose, lifestyle modifications linked to physical activity, eating habits, smoking cessation, stress management and moderate alcohol consumption.

3.2.7 Laboratory blood pressure assessment

The laboratory blood pressure (systolic and diastolic) will be obtained in two days, at a similar time, using the OMRON automatic equipment, model 742HEM. On each day, three measurements will be performed with an interval of one minute between them, with the cuff placed on the left arm, elevated to the height of the midpoint of the sternum. If the variation of these three measurements is greater than 4 mmHg for systolic and/or diastolic blood pressure, new measurements will be performed until this established criterion is met. The average value between the measurements obtained on the different days will be recorded as a reference value at the different moments of the study.

3.2.8 Assessment of medication adherence

Adherence to the medication will be assessed using the Morisky's Therapeutic Adherence Scale of eight items, translated into Portuguese and validated by Oliveira-Filho et al.²⁰, in the pre and post-intervention moments.

3.2.9 Assessment of habitual physical activity

Habitual physical activity will be assessed using accelerometry, using devices of the GT3X and GT3X+ models (Actigraph Pensacola, FL, USA) and the Actilife software (Actigraph Pensacola, FL, USA). Each participant will be instructed to use the accelerometer for seven consecutive days, removing it only to sleep, shower or perform water activities. The device will be placed on an elastic belt and fixed on the right side of the hip. Data will be collected at a frequency of 30 Hz and analyzed in 60 s epochs. Periods with consecutive zeros for 60 min or more (with a 2 min tolerance) will be interpreted as non-use time

and excluded from the analysis ²¹. For analysis purposes, a minimum of 10 hours of daily activity recordings, for at least four days, three weekdays and one weekend day will be considered valid data. The average time spent in each intensity of physical activity will be calculated from the cut-off points proposed by Freedson et al. ²², considering sedentary behavior as 0 – 99 counts/min, light physical activities as 100-1951 counts/min, moderate physical activities as ≥ 1952 counts/min and vigorous or very vigorous activities as ≥ 5725 counts/min. Data will be analyzed in min/day, adjusted by number of days of use and daily time of use.

3.2.10 Lifestyle assessment

Lifestyle will be evaluated using an adapted version of the Fantastic questionnaire which includes questions related to the following components: nutrition, physical activity, preventive behavior, social relationships and stress control. For each question, patients will answer whether such behavior is not part of their lifestyle, rarely matches, almost always matches, or always matches.

3.2.11 Evaluation and patient satisfaction with the application

At the end of the intervention, patients undergoing the GA will be invited to answer an adapted version of the assessment scale for *smartphone applications* for health care, proposed by Jim and Kim ²⁴, which contains 23 items in total, related to the assessment of content, objectivity, interface design, writing style and technology, with response options ranging from zero (not at all) to four (a lot), generating an overall score. From there, all adjustments that are considered relevant will be made so that the final version of the application will be available on Apple iTunnes and Google Play.

3.2.12 Statistical analysis plan (SAP)

Initially, the normality and homogeneity of variance will be analyzed using the Shapiro-Wilk and Levene tests, respectively. For data that do not have a normal distribution, logarithmic transformation will be performed. Student 's t test for independent samples and the chi-square test will be used to compare the groups at the pre-intervention moment, regarding continuous and categorical variables, respectively.

For the Intra and inter-group comparisons of quantitative and qualitative variables, the method of generalized estimation equations will be used (group: GA and GC; time: pre and post-intervention assessments; interaction (group vs. time), after confirming the appropriate assumptions. In all analyses, when a significant effect is verified, the Newman-Keuls post-hoc test will be used, with a P value <0.05 being considered significant.

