3.2 Effectiveness testing

3.2.1 Participants

This stage of the study will involve the performance of a randomized and controlled clinical trial that will be conducted at the Sports Center of the Federal University of Santa Catarina, Florianópolis, SC. Based on a previous behavior change study¹⁹, taking systolic blood pressure as a reference, taking into account an effect size of 0.8, power of 80% and alpha error of 0.05, the estimated sample size is 52 participants (26 per group). The recruitment of these participants will be based on the dissemination of the research in the local media (radio, newspapers, internet) and in social groups, distribution of pamphlets and posting of posters in the vicinity of the evaluation sites.

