3.2.2 Screening

As inclusion criteria, participants must be over 18 years old, have a clinical diagnosis of SAH³, have been using antihypertensive medication for more than three months, and cannot be involved in the regular practice of physical activities. In addition, participants must have a *smartphone*, they must not have cognitive disabilities that limit the understanding and use of an application and/or physical limitations that make it difficult to practice physical activities. Changes in the type and/or dose of antihypertensive drugs used during the study will be considered as exclusion criteria.

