3.2.4 Experimental Design

Participants will be submitted, before the start of the intervention (pre-intervention), to laboratory blood pressure assessments, adherence to drug treatment, physical activity and lifestyle. Afterwards, the GC will participate in an informative lecture on healthy habits and general aspects of SAH control and treatment, while the GA will be submitted to the use of the application for eight weeks. At the end of these eight weeks of intervention (post-intervention), the participants of both groups will be reassessed in all the items analyzed at the pre-intervention moment. It is noteworthy that the researchers involved with the evaluations and data analysis will be blinded regarding the randomization of the participants.

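### The group × time GEE in 3.2.12 leaves working correlation, analysis population and missing eight-week values unstated; two natural readings bias the SBP effect, in opposite directions, if loss depends on baseline SBP differently by arm.

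*Combined protocol and SAP*

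**What the plan says.** The Combined protocol and SAP, section 3.2.12, specifies one model for quantitative and qualitative outcomes alike: "the method of generalized estimation equations will be used (group: GA and GC; time: pre and post-intervention assessments"), together with their interaction. Its significance rule is "with a P value <0.05 being considered significant". Section 3.2.4 provides a single post-baseline assessment: "At the end of these eight weeks of intervention (post-intervention), the participants of both groups will be reassessed". Anyone who misses that visit therefore has at most a baseline value.

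Section 3.2.1 sizes the trial on SBP, "taking into account an effect size of 0.8, power of 80% and alpha error of 0.05", and concludes that "the estimated sample size is 52 participants (26 per group"), with no allowance for loss. Section 3.2.2 adds a route out of the trial after entry: "Changes in the type and/or dose of antihypertensive drugs used during the study will be considered as exclusion criteria". It does not say what happens to those participants' data.

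No section states the working correlation, who is analysed, how a missing eight-week value is treated, or any sensitivity analysis.

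**The concern.** With two time points and a saturated group × time mean model, the unstated choices decide what is estimated once participants are lost.

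- **Working independence, baselines kept.** Each arm's change is the mean post value of those who returned minus the mean baseline of everyone. These are different sets of people.
- **Completers only.** The people are the same before and after. But if those with high baselines leave one arm, regression to the mean no longer cancels between arms.

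The documents give a reason to expect loss that is related to BP and differs by arm. Under section 3.1, the app responds to high entered readings by suggesting a medical consultation about possible changes in medication, and section 3.2.2 treats a drug change as an exclusion. The control group has a single lecture (section 3.2.6) and no such BP-triggered prompt. The plan could thus remove participants with higher BP preferentially from the app group. Under working independence, that would make an inert app look effective.

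**Working it through.** **1. The plan's own figure.** For effect size 0.8, two-sided alpha 0.05 and 80% power, the normal approximation gives n per arm = 2(1.960 + 0.842)²/0.8² = 24.5, so 25. The two-sample t-test version gives 25.52, so 26 per arm and 52 in total (power 80.7%). The stated sample size is reproduced, with no inflation for loss.

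**2. Assumed inputs.** The documents give no SD, pre-post correlation or loss rate. Assumed: SBP SD 15 mmHg at both visits; correlation ρ 0.5 to 0.7; control loss 10%, unrelated to BP; GA loss 20% or 30%, with log-odds rising by 1.0 per SD of baseline SBP (range 0.7 to 1.5); no true effect. Negative bias favours the app.

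**3. Formulae.** Let d be the mean baseline of GA returners minus that of all GA participants. In the control group d = 0. With equal SDs, the returners' post mean shifts by ρd. The bias in the group × time effect is then:

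- working independence, all baselines kept: ρd
- completers' change: ρd − d = −(1 − ρ)d
- likelihood model, all baselines kept: ρd − ρd = 0

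**4. Numbers.** At slope 1.0, integrating the logistic loss model over a normal baseline gives d = −0.173 × 15 = −2.60 mmHg (20% loss) and −0.253 × 15 = −3.79 mmHg (30% loss).

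| GA loss | ρ | Independence, ρd | Completers, −(1 − ρ)d |
|---|---|---|---|
| 20% | 0.5 | −1.3 | +1.3 |
| 20% | 0.6 | −1.6 | +1.0 |
| 20% | 0.7 | −1.8 | +0.8 |
| 30% | 0.5 | −1.9 | +1.9 |
| 30% | 0.6 | −2.3 | +1.5 |
| 30% | 0.7 | −2.7 | +1.1 |

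Over slopes 0.7 to 1.5, d runs from −1.95 to −4.90. Independence bias therefore runs from 0.5 × (−1.95) = −1.0 to 0.7 × (−4.90) = −3.4 mmHg.

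**5. Simulation.** With 26 per arm over the same grid, independence bias was −1.1 to −3.6 mmHg. The false-positive rate was 5.4% to 13%, even with a small-sample variance and t reference. A baseline-adjusted likelihood-type analysis stayed within 0.15 mmHg, with error 4.8% to 5.6%. At ρ 0.6, slope 1.0 and losses of 10% versus 30%, the biases were: independence −2.2, completers +1.5, exchangeable GEE −0.1, mixed model 0.0.

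**6. Other loss patterns** (large-sample simulation, ρ 0.6, SD 12 to 18, slope 1.0; bias in mmHg).

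| Loss pattern | Independence | Exchangeable GEE | Mixed model |
|---|---|---|---|
| Unequal rates, unrelated to BP | 0.0 | 0.0 | 0.0 |
| Same dependence on baseline in both arms, unequal rates | −0.6 to −1.8 | about −0.1 or smaller | 0.0 |
| Opposite dependence on baseline in the two arms | −1.9 to −3.7 | −0.1 to −0.3 | 0.0 |
| Depends on unseen week-8 SBP, GA only | −2.1 to −4.6 | −1.4 to −3.0 | −1.4 to −3.0 |

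In the last pattern at 26 per arm (SD 15, losses 10% versus 30%), the biases were −3.8 for independence, −2.5 for exchangeable GEE and mixed model alike, and −1.5 for completers.

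**The case against.** The strongest reply is that section 3.2.12 is underspecified rather than wrong. It does not choose working independence, names no software whose default could be checked, and does not say that baseline-only participants are kept. That is correct, so the point is conditional. It still matters, because independence with baselines kept and completers only are both natural readings, both are biased under baseline-related loss, and the sign depends on which is used.

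A reader might go on to infer four stronger things that the documents and the calculations do not support:

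- **That GEE is valid here only if loss is unrelated to BP.** An exchangeable or unstructured working correlation with all baselines kept is within about 0.3 mmHg under baseline-related loss.
- **That different loss rates by themselves bias the effect.** They give 0.0 mmHg under every method; loss must also depend on BP. The burden of using the app, taken alone, establishes no such link.
- **That a mixed model removes the problem.** It does so only when loss depends on observed baseline BP. When loss depends on week-8 BP, it reduces the bias relative to independence, performs like exchangeable GEE, and can be worse than completers only. If participants with drug changes are dropped entirely, it reduces to the completers' change and corrects nothing.
- **That 1 to 4 mmHg is a property of this trial.** Every input behind it is assumed.

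The preference for a mixed model over an exchangeable GEE is therefore modest. Part of its gain in precision comes from the common baseline mean, which would help with complete data too.

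**Conclusion.** The concern holds in conditional form. Section 3.2.12 leaves open choices that move the SBP effect by roughly 1 to 4 mmHg towards the app (working independence, all baselines kept), or by about 1 to 2 mmHg against it (completers only), when GA participants with higher baseline SBP are likelier to be lost. If those with lower baselines are lost instead, both signs reverse. At the assumed SD the planned effect is 0.8 × 15 = 12 mmHg, so a bias of 3.6 mmHg would be 3.6/12 = 30% of it.

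These sizes rest on SD 15 mmHg, ρ 0.5 to 0.7, losses of 20-30% versus 10%, and a dependence of loss on baseline SBP in GA only. With loss unrelated to BP, or with the same loss mechanism and rate in both arms, the bias is about zero. The plan should be changed on this point, although GEE as such is not an invalid method here.

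**What to change.** In section 3.2.12:

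1. For continuous outcomes, specify a linear mixed model fitted by REML, with unstructured 2×2 covariance, a common baseline mean and a group effect at post-intervention only. Include every randomised participant with any value.
2. If GEE is kept, including for the qualitative outcomes, rule out working independence for SBP and the other continuous outcomes. Use an exchangeable or unstructured correlation and keep all baselines.
3. State how the data of participants whose antihypertensive drugs change (section 3.2.2) are analysed, and reconcile that with the analysis population.
4. Report losses and exclusions, with reasons, by arm and by baseline SBP.
5. Add a delta-adjusted sensitivity analysis, shifting the missing week-8 values by arm over a stated range, to cover loss that depends on unobserved BP.

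The cost is SAP wording and a little more analysis on the same data, with no extra participants. The downside is reliance on missing-at-random and covariance assumptions; item 5 probes the first of these.

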3.2.3 Randomization

After the pre-intervention assessments, participants will be randomized into two groups: app group (GA) and control group (CG). This randomization will be performed in blocks, according to sex and pre-intervention blood pressure, from a table of random numbers, by researchers who are not directly involved with the recruitment of participants and with data collection.

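### The planned GEE names no small-sample inference: by the usual default, a 5% test at 26 per arm runs at about 6.0% for continuous outcomes other than blood pressure

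*Combined protocol and SAP*

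**What the plan says.** Section 3.2.12 says that "the method of generalized estimation equations will be used". It applies this to both within- and between-group contrasts and to both continuous and categorical outcomes, with terms for arm, assessment time and their interaction. The threshold is set "with a P value <0.05 being considered significant". The section does not give the working correlation, the variance estimator (model-based, sandwich or corrected sandwich) or the reference distribution (normal/chi-square or t/F). It does not mention confidence intervals.

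Section 3.2.1 sizes the trial on systolic blood pressure, "taking into account an effect size of 0.8, power of 80% and alpha error of 0.05", and concludes that "the estimated sample size is 52 participants (26 per group"). No dropout allowance is given. Section 3.2.4 has one pre- and one post-intervention assessment, so each participant contributes two observations.

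Section 3.2.3 says that randomisation is "performed in blocks, according to sex and pre-intervention blood pressure". The outcomes in sections 3.2.8 to 3.2.10 (medication adherence, accelerometer activity, lifestyle) are not randomisation factors.

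**The concern.** The sandwich standard error used with GEE is justified when there are many independent clusters. Here each cluster is a participant, and there are at most 52. At that size the uncorrected estimator is biased low, and the usual Wald test compares it with 1.96 rather than a t quantile. Both errors push towards declaring a difference. Fewer participants may be analysed than are randomised: section 3.2.2 treats changes in antihypertensive type or dose as an exclusion criterion, and section 3.2.9 requires a minimum number of valid accelerometer days.

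At stake is whether the 5% threshold means 5%. The answer depends on the outcome, because stratifying on blood pressure also changes how the unadjusted blood-pressure test behaves.

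**Working it through.** **Inputs.** From the documents: 26 per arm, two observations per participant, a group-by-time model, P<0.05. Assumed: a two-sided test; the default inference (uncorrected sandwich, normal reference); roughly normal outcomes; complete data. Losses to 21 or 18 per arm are illustrative, since the documents give no dropout figure.

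**1. The plan's own figure.** The normal approximation gives n = 2(1.960 + 0.842)²/0.8² = 24.5, so 25 per arm. An exact two-sided t test has power 79.1% at 25 per arm and 80.7% at 26. The planned 26 per group is reproduced. A one-sided test would need about 20, so two-sided is the consistent reading.

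**2. What the GEE term is.** With two time points and complete data, the group-by-time coefficient is the difference between arms in mean change. Its uncorrected sandwich standard error divides by n rather than n−1 within each arm, so it equals √((n−1)/n) times the unbiased one. Then:

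- false-positive rate = P(|t on 2n−2 df| > 1.96·√((n−1)/n))
- interval width relative to correct = 1.96·√((n−1)/n) / t(0.975, 2n−2)

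| n per arm | √((n−1)/n) | effective cut-off | correct t | width ratio | false-positive rate |
|---|---|---|---|---|---|
| 26 (planned) | 0.981 | 1.922 | 2.009 | 0.957 | 6.0% |
| 21 (assumed) | 0.976 | 1.913 | 2.021 | 0.946 | 6.3% |
| 18 (assumed) | 0.972 | 1.905 | 2.032 | 0.937 | 6.5% |

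Simulation of the 26-per-arm case (200,000 null trials) gives 6.03%, and a GEE fitted with robust standard errors gives 6.0% (4,000 trials). Under stratified randomisation, a continuous outcome unrelated to blood pressure gives 5.8-6.2%. A strongly skewed outcome gives about 5.8%.

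**3. Blood pressure.** Stratifying on baseline blood pressure makes the arms more alike at baseline than the unadjusted standard error assumes. With pre-post correlation ρ and equal variances, baseline accounts for a share (1−ρ)/2 of the variance of change: 25% at ρ = 0.5 and 15% at ρ = 0.7. A median split captures 2/π = 0.637 of the variance of a normal baseline. Balancing therefore removes 0.25 × 0.637 = 15.9%, or 0.15 × 0.637 = 9.5%, of the true variance of the contrast. The effective cut-off rises from 1.922 to 1.922/√0.841 = 2.096, or 1.922/√0.905 = 2.021. On 50 df these give false-positive rates of about 4.1% and 4.9%. Simulation of the same set-up gives 4.1-4.8%.

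**4. Binary outcomes.** Simulated rates range from 4.9% to 5.8%. The lower figures come from only 1,500 trials, where the Monte Carlo standard error is √(0.05 × 0.95/1,500) = 0.56 points.

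**5. Remedies at 26 per arm.** For the unadjusted contrast in step 2:

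- Kauermann-Carroll-type standard error with t on 50 df: 5.0%; with a normal reference: 5.6%.
- Mancl-DeRouen-type with t on 50 df: 4.6%.

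A linear model of the week-8 value on arm, baseline and strata with t-based inference gives 4.7-5.2% in stratified simulation. The intervals for the unadjusted contrast widen by 1/0.957 − 1 = 4.5% over the uncorrected default.

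**The case against.** The strongest reply is that the plan never says it will use the uncorrected sandwich with a normal reference. That stands: the defect depends on a default that section 3.2.12 neither states nor excludes.

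The second reply is that, for the outcome on which the trial is sized, the planned test is conservative. That also stands. A reader might infer that the analysis as a whole leans towards finding the app effective. The documents do not support this, because blood pressure is a randomisation factor and its unadjusted test runs below 5%.

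A reader might also take 6.5% or more as the rate at the planned size. For the between-group contrast, 6.5% needs either a loss to about 18 per arm, which is assumed, or a model adjusted for baseline and strata but left uncorrected, which the plan does not specify. Within-arm comparisons would reach 6.6% at 26 per arm if tested by Wald z, but section 3.2.12 sends follow-up comparisons to Newman-Keuls, so that figure cannot be assigned to the plan.

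Finally, the plan promises no confidence intervals, so the statement about width concerns only intervals that may be reported.

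**Conclusion.** The point holds in a limited form. If default GEE inference is used, the between-group test for roughly normal continuous outcomes not stratified on runs at about 6.0% rather than 5% at 26 per arm, and any interval is about 4% too narrow. With assumed losses to 18-21 per arm, the figures are about 6.3-6.5% and 5-6%. The unadjusted blood-pressure test runs at about 4.1-4.8%, assuming a median split and a pre-post correlation of 0.5-0.7. No clear inflation is shown for binary outcomes.

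The departure is about one percentage point in either direction. It would matter only for a borderline result, so this is a minor improvement, worth making because one analysis choice corrects both errors.

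**What to change.** In section 3.2.12:

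- **Continuous outcomes.** Analyse the week-8 value in a linear model on arm, baseline value and the randomisation strata (sex, baseline blood pressure), with t-based tests and intervals. This holds about 5% under approximately normal, equal-variance errors. It is not exact for the bounded adherence and lifestyle scores.
- **Where GEE is kept.** State a Kauermann-Carroll-type corrected covariance with a t reference. Mancl-DeRouen with t is an alternative, but is slightly conservative here (about 4.6%). The two should not be treated as interchangeable.

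The cost is a few lines of text. The model uses measurements already planned and factors already used in randomisation. For outcomes not stratified on, P values become slightly larger and any intervals about 4.5% wider at 26 per arm than under the uncorrected default. Nothing in recruitment, assessment or treatment changes.

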2.2 Specific Objectives

The specific objectives of the study will be:

a) develop a prototype application aimed at treating patients with SAH, including tools to improve medication adherence, monitor blood pressure values, monitor and promote physical activity and healthy lifestyle habits;

b) test the effectiveness of this application on laboratory systolic and diastolic blood pressure, adherence to drug treatment, habitual physical activity and lifestyle in hypertensive adults.

c) test the usability of this application on hypertensive adults.

3 Materials and methods

The study will be developed in three stages, according to the objectives outlined. Initially, a prototype of a cellphone application will be developed to help Brazilian adults diagnosed with SAH, with tools related mainly to medication adherence, promotion of physical activity and monitoring of blood pressure values, in addition to health tips (food, smoking, alcoholism and stress management). Subsequently, this prototype will be made available to a group of adult hypertensive patients so that the effectiveness of this application can be tested on laboratory blood pressure values, medication adherence and lifestyle aspects, including physical activity and, subsequently, physical activity. Application usability will be tested. Subsequently, after making the necessary adjustments, the application will be made available on the Apple iTunes and Google Play platforms and disseminated in groups of Basic Health Units and in the media (advertisements on television, newspaper, radio). From there, the number of downloads and the grade assigned to user reviews (one, two, three or

four stars) will be evaluated, according to the user's sociodemographic characteristics (gender, age, place of residence).

App Development

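### The SAP does not say which GEE term tests the app, and it prescribes Newman-Keuls, which suits neither paired pre/post means nor qualitative outcomes

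*Combined protocol and SAP*

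**What the plan says.** The objective in 2.2 is to "test the effectiveness of this application on laboratory systolic and diastolic blood pressure, adherence to drug treatment, habitual physical activity and lifestyle". Section 3.2.1 sizes the trial "taking systolic blood pressure as a reference, taking into account an effect size of 0.8, power of 80% and alpha error of 0.05", giving 26 per group. Under 3.2.4, "the participants of both groups will be reassessed in all the items analyzed at the pre-intervention moment", so every outcome is a pre/post pair on the same person.

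The analysis is in 3.2.12: "For the Intra and inter-group comparisons of quantitative and qualitative variables, the method of generalized estimation equations will be used", with group, time and their interaction as terms. The follow-up rule is: "In all analyses, when a significant effect is verified, the Newman-Keuls post-hoc test will be used, with a P value <0.05 being considered significant".

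The interaction is therefore in the model. Neither 3.2.12 nor any other section says that it, or any other contrast, is the test of the app. Two further things are left open: whether the post-hoc step compares all four group-by-time means or only the levels of the effect found, and which error term it uses. The qualitative variables are not listed.

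**The concern.** Whether the app works is a between-group question. The follow-up rule gives every significant term the same consequence, including a time effect shared by both arms. A shared change is plausible because controls "will participate in a single lecture, in the first week of the intervention" that covers medication adherence and lifestyle; the documents do not give its size. If a shared fall opens the post-hoc step and the app group's change is significant while the control group's is not, a reader could take that as an app effect, and nothing in the plan rules this out.

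The prescribed test is also a poor fit in its own right. Two analysts following 3.2.12 could choose different scopes and error terms and reach different conclusions from the same data.

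**Working it through.** **1. The plan's own figure.** Inputs from 3.2.1: effect size 0.8, power 80%, alpha 0.05 (two-sided assumed, as sidedness is not stated). A two-sample t-test needs 25.52 per arm, rounded up to 26, or 52 in total. Power at 26 per arm is 80.7%. The stated figure reproduces.

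**2. After a main effect.** Group and time each have two levels. For two means the studentized-range critical value is the t or z value times √2: 1.96 × 1.414 = 2.77. Newman-Keuls then only repeats the test already done, so it can matter only across the four cells.

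**3. Why pairing matters.** With unit SD and pre-post correlation r, the variance of a within-arm mean change is 2(1−r)/26. Treating the cells as independent uses 2/26, so the standard error is too large by 1/√(1−r): 1.20, 1.41 and 1.83 at r = 0.3, 0.5 and 0.7. In simulation with no true change, the within-app-group rejection rate is 0.0-0.4% instead of 5%. At a 0.5 SD change it detects that change in 15-23% of trials, against 54-88% for a paired t-test. A within-subject error term makes the opposite mistake: it understates the week-8 between-arm standard error by √(1−r).

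**4. False findings.** Assumptions, none in the documents: no app effect, complete data, r of 0.3-0.7, and the same fall in both arms. There were 20,000 simulated trials per setting with 26 per arm.

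*Four-cell testing only after a significant interaction:* app-group-only significance is at most 3.0%, and a false week-8 difference at most 2.8%.

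*Any significant term opens four-cell testing:* percentage of trials with the app group significant and the control group not, at r = 0.3 / 0.5 / 0.7:

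| Shared fall (SD) | Independent-cells error | Pair-specific GEE error |
|---|---|---|
| 0.2 | 1.7 / 0.9 / 0.2 | 5.2 / 5.4 / 5.6 |
| 0.35 | 6.3 / 4.6 / 2.2 | 12.7 / 13.7 / 13.0 |
| 0.5 | 15.0 / 13.7 / 10.3 | 19.9 / 19.7 / 15.0 |
| 0.7 | 19.4 / 18.9 / 18.1 | 17.0 / 12.1 / 7.0 |
| 0.9 | 9.7 / 7.3 / 4.5 | 5.8 / 2.8 / 1.0 |

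The false week-8 between-group rate over the same settings is 1.5-5.3% (independent cells) and 2.3-6.1% (pair-specific). With no shared fall, the app-group-only pattern is 0-2%.

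**5. Is Newman-Keuls the source of that pattern?** A separate paired t-test in each arm, without Newman-Keuls, gives it in 18.2, 21.9 and 25.2% of trials at a 0.3 SD fall, and in 24.5, 21.3 and 9.8% at 0.5 SD. So it is not.

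**6. A single named test.** Simulated level is 4.7-5.4% for the baseline-adjusted week-8 test, 4.7-5.3% for group x time with a t reference, and 5.6-6.3% for an uncorrected GEE Wald test.

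**7. Power at 26 per arm.** Section 3.2.1 does not say which SD the 0.8 refers to.
- Post-value SD: the standardised effect is 0.8/√(2(1−r)) for group x time and 0.8/√(1−r²) for the adjusted test.
- Change-score SD: it is 0.8 for group x time and 0.8·√(2/(1+r)) for the adjusted test.

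| Meaning of 0.8 | Test | r = 0.3 | r = 0.5 | r = 0.7 |
|---|---|---|---|---|
| Post-value SD | Group x time | 67% | 81% | 95% |
| Post-value SD | Adjusted week-8 | 84% | 90% | 98% |
| Change-score SD | Group x time | 81% | 81% | 81% |
| Change-score SD | Adjusted week-8 | 94% | 90% | 87% |

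**The case against.** The plan is closer to right than a quick reading suggests. Group x time is listed, between-group comparison is announced, and in a two-by-two pre/post trial the interaction is the conventional test of a difference in change. A reader might infer that the between-group test is missing. It is not; it is undesignated.

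A main effect with two levels leaves nothing to separate, so four-cell testing most naturally follows a significant interaction, and there both errors are small. This stands, and it is why the larger figures cannot be presented as what the plan will produce. They need the broader reading, which the words allow but do not state.

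A reader might also infer that the plan yields false week-8 differences in up to about a quarter of null trials. Simulated rates of 4-28% do arise, but only with a within-subject error term applied to a between-subject comparison. The SAP specifies GEE, whose contrasts carry their own standard errors, so that choice does not fit the stated method.

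Finally, the app-group-only pattern comes from comparing within-arm tests, so deleting Newman-Keuls alone would not remove it. The SAP does not tell anyone to read that pattern as an app effect. Both points stand. They make naming the decisive contrast the more important half of the fix.

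None of this makes Newman-Keuls suitable for paired or qualitative data, or supplies the missing designation.

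**Conclusion.** The point holds in limited form. Section 3.2.12 designates no decisive test and prescribes a follow-up test that suits neither the paired means nor the qualitative outcomes. That rests on the text alone and is firm.

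The size of the harm is conditional. It is about 3% or less if only the interaction opens four-cell testing. If any term does, a misleading app-group-only pattern appears in about 0-19% of null trials (independent cells) or 1-20% (pair-specific GEE errors), with a near-nominal week-8 between-group error. These ranges depend on the assumed correlation and shared fall, and they illustrate the risk rather than estimate it for this trial. The documents do not support a claim that the between-group false-positive rate is grossly inflated, or that the sample size is wrong. This should be fixed before analysis, but it does not undermine the design.

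**What to change.** In 3.2.12, name one confirmatory test for SBP, the outcome used for sizing, at two-sided 0.05.

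- **Preferred:** the between-group difference in week-8 SBP, adjusted for pre-intervention SBP and sex, with a t reference. This follows 3.2.3: "This randomization will be performed in blocks, according to sex and pre-intervention blood pressure".
- **If GEE stays primary:** the group x time contrast, with a small-sample-corrected standard error or a t reference. Its level is sound and it keeps the sponsor's method, so preferring the adjusted test is a matter of efficiency. If 0.8 is in post-value SDs and the correlation is 0.3, group x time has about 67% power, below the planned 80%.
- Do not run both as confirmatory.

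Replace Newman-Keuls with model-based contrasts and 95% CIs, using a link suited to each outcome type. Present within-group changes as descriptive only, and label the other outcomes in 2.2 as secondary. State in 3.2.1 which SD the 0.8 refers to.

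The cost is SAP wording; no new data, visits or participants are needed. The downsides are that fewer results can be called significant and that the adjusted test uses only participants with a week-8 SBP value.
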